5.3.2 Improvement from Baseline in Worst Incontinence Grading

Worst Incontinence Grading is derived from:

- The response to "Worst Leakage during the Day" and "Worst Leakage during the Night" from the 5-day Week Diary, and is equal to the worst outcome from both daytime and nighttime responses during a diary day.
- The responses to "Worst Leakage Severity" every time it is reported in the 2-day Weekend Episodic Diary. The worst response to the questions given during a diary day will be used for analysis.

Possible outcomes are: Dry; Slightly Wet; Moderately Wet; and Fully Wet.

Dry will be derived from the question on the 5-day Week Diary: "How was your day/night", and from the 2-day Episodic Weekend Diary if no leakages are reported during a diary day.

For each subject and visit the worst incontinence grade will be determined as the worst grading over the valid diary days preceding the study visit.

Improvement:

For Visit x (x=3, 4, 5, 6 and 7) the average over the valid week and weekend diary days will be calculated from the score of what was the worst leakage during the day", *i.e.*, 0 - Dry, 1 - Slightly Wet; 2 - Moderately Wet; and 3 - Fully Wet:

Worst Incontinence Grade at Visit x =

```
Sum of Worst Incontinence Gradings over the Valid Diary Days prior to Visit x
Number of Valid Diary Days
```

For each subject, improvement at Visit x if:

Worst Incontinence Grade (Visit x) - Worst Incontinence Grade (Visit 3 [Baseline]) < 0.

5.3.3 Mean Volume Voided as a Percentage of Expected Bladder Capacity

To calibrate the mean volume voided with bladder size, the ratio of mean volume voided to the subject's EBC (= $[age+1] \times 30$ in mL for children and 400 mL for adolescents) will be calculated at baseline and post-baseline study visits and expressed as a percentage. These ratios will be summarized together with the change from baseline by age group and overall.

The following variables will be summarized, for each age group and overall, by treatment group at each visit using number and percentage of subjects in the following categories:

Ratio of mean volume voided to EBC (%): ≤50%, >50% to ≤75%, >75% to ≤100%, >100%

• Change from baseline in ratio of mean volume voided to EBC (%): <0%, 0% to <15%, 15% to <30%, ≥30%

5.3.4 Mean Number of Micturitions per 24 hours, Adjusted for Fluid Intake

For this endpoint the voided volumes will be taken as surrogate for the fluid intake.

In Sender Herschorn *et al.*, (2017) page 56 Materials and Methods, the following subdivision is presented of the number of micturitions at a visit, say visit x.

Number of Micturitions at Visit x (x = 4, 5, 6, and 7) =

Total Volume Voided (Visit x) / Mean Volume Voided (Visit x) =

[Total Volume Voided (Baseline) + Δ Total Volume Voided]/Mean Volume Voided (Visit x) =

Total Volume Voided(Baseline) / Mean Volume Voided(Visit x) +

 Δ Total Volume Voided / Mean Volume Voided(Visit x),

where Δ is the difference in total volume voided between Visit x and Baseline [=Total Volume Voided (Visit x) – Total Volume Voided (Baseline)].

This can be viewed as a partition of Number of Micturitions at Visit x into 2 parts as follows:

- Total Volume Voided (Baseline) / Mean Volume Voided (Visit x) is the number of micturitions per 24 hours that would be required at Visit x to void the total daily volume, if this total volume remains unchanged from baseline, that is, if treatment did not affect subjects' fluid intake.
- Δ Total Volume Voided / Mean Volume Voided(Visit x) is the additional number of micturitions per 24 hours (vs baseline) required to void the extra fluid intake.

For each subject, the Mean Change in Number of Micturitions per 24 hours at Visit x (x=4, 5, 6, and 7), adjusted for fluid intake will be calculated as:

Total Volume Voided at Visit x -Total Volume Voided at BaselineMean Volume Voided per Micturition at Visit x

Example:

A subject voided the following volumes:

- At baseline, Saturday: 200 ml, 200 ml, 200 ml, 200 ml and 200 ml, and Sunday: 200 ml, 200 ml, 200 ml and 200 ml
- At visit x, Saturday: 250 ml, 250 ml, 250 ml and 250 ml, and Sunday: 250 ml, 250 ml and 250 ml

This results in:

Total Volumes Voided per 24 hours at baseline and at visit x are 900 ml and 875 ml, respectively. Mean Volume Voided per 24 hours at visit x is 250 ml,

Total Volume Voided (baseline) / Mean Volume Voided (visit x) = 900 ml / 250 ml = 3.6, which means that 3.6 micturitions per 24 hours would be required at visit x to void the same total volume as voided at baseline (3.6 x 250 = 900 ml). This is the expected mean number of micturitions per 24 hours at visit x.

Mean number of micturitions at baseline and at visit x are 4.5 and 3.5, respectively. Mean difference in the number of micturitions per 24 hours adjusted for fluid intake compared to expected mean number of micturitions per 24 hours at visit x is (875-900)/250 = -0.1.

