	• Categorized mean volume voided per micturition as a percentage of expected bladder capacity (results and changes from baseline).			
	• Change from baseline at the end of the 12-week treatment period adjusted for fluid intake:			
	 Mean number of micturitions per 24 hours Change from baseline at the end of the 12-week treatment period (adolescents only): Mean number of micturitions per 24 hours Mean number of daytime micturitions per 24 hours Mean volume voided per 24 hours Mean number of incontinence episodes per 24 hours Maximum volume voided 			
	 Number of dry (incontinence-free) days per 7 days at the end of the 12-week treatment period (adolescents only) Mean number of daytime grade 3 or 4 (PPILIS) 			
	• Mean number of daytime grade 3 or 4 (PPIUS) urgency episodes per 24 hours (adolescents only)			

AE: adverse event; ECG: electrocardiogram; OAB: overactive bladder; PPIUS: patient perception of intensity of urgency scale; PVR: post void residual.

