5.2.1 Mean Volume Voided per 24 hours

Mean volume voided is derived from "Pee Volume" of the 2-day Weekend Episodic Diary.

For each subject, the mean volume voided per day will be calculated as the sum of the volumes voided on that (valid diary) day divided by the number of times a volume was recorded on that day in the 2-day Weekend Episodic Diary.

The mean volume voided at Visit x (x=4, 5, 6, and 7) will be calculated as the mean value of the mean volumes voided on each of the two days

If volumes are recorded on 1 single (valid) day of the 2-day Weekend Episodic Diary, then the mean volume will be the sum of all available volumes of that day divided by the number of times a volume was recorded.

If no volumes are recorded on either (valid) measuring day, then the mean volume will be missing.

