6.4.3 Analysis of Exploratory Endpoints

Data of the following explorative endpoints will be summarized, separately, for pediatric subjects:

- Percentage of subjects with a reduction in daytime incontinence episodes (< 50% reduction [non-responder], 50% [partial responder] and 100% [responder])
- Improvement from baseline in worst incontinence grading. Average over 7 days will be calculated of the score of "What was your worst leakage during the day": 1 Slightly Wet; 2 Moderately Wet; and 3 Fully Wet
- Mean number of micturitions per 24 hours, adjusted for fluid intake:
 - Number of micturitions per 24 hours that would be required at week 12/EoT to void the same total volume as voided at baseline
 - Difference in mean number of micturitions per 24 hours adjusted for fluid intake compared to the expected mean number
- Mean volume voided per micturition as a percentage of expected bladder capacity
- Categorized mean volume voided per micturition as a percentage of expected bladder capacity (results and changes from baseline).

Efficacy endpoints for adolescents will be analyzed descriptively.

- Change from baseline at the end of the 12-week treatment period (adolescents only):
 - Mean number of micturitions per 24 hours
 - Mean number of daytime micturitions per 24 hours
 - Mean volume voided per 24 hours

- Maximum volume voided
- Mean number of incontinence episodes per 24 hours
- Number of dry (incontinence-free) days per 7 days at the end of the 12-week treatment period (adolescents only)
- Mean number of daytime grade 3 or 4 on Patient Perception of Intensity of Urgency Scale (PPIUS) urgency episodes per 24 hours (adolescents only) will be summarized by treatment group and visit.

Correlations between the primary endpoint and mean volume voided, as well as incontinence episodes, will be explored. Scatter plots will be presented to access the correlation between the primary end point and mean volume voided and number of incontinence episodes at visit 7/week 12.

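### Two exploratory derivations need correcting: SAP 5.3.4 names the fluid component as the fluid-adjusted change, and SAP 5.3.1 compares raw leak totals across diaries of unequal length (minor)

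*SAP*

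**What the plan says.** **Fluid adjustment.** SAP 5.3.4 uses voided volume as a stand-in for intake. It splits the number of micturitions at a visit into two terms, where TVV is total volume voided per 24 hours and MVV is mean volume per void:

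- TVV(baseline)/MVV(visit): the voids needed if volume had stayed at its baseline level.
- [TVV(visit) - TVV(baseline)]/MVV(visit): this "is the additional number of micturitions per 24 hours (vs baseline) required to void the extra fluid intake".

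It then gives a formula for a change: "For each subject, the Mean Change in Number of Micturitions per 24 hours at Visit x (x=4, 5, 6, and 7), adjusted for fluid intake". That formula is the second term. The worked example states "Mean number of micturitions at baseline and at visit x are 4.5 and 3.5, respectively", finds 3.6 expected voids at baseline volume, and ends with a difference from the expected number that "is (875-900)/250 = -0.1".

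SAP 6.4.3 plans two summaries: "Number of micturitions per 24 hours that would be required at week 12/EoT to void the same total volume as voided at baseline" and "Difference in mean number of micturitions per 24 hours adjusted for fluid intake compared to the expected mean number". SAP 2.1 (Table 1) also lists, for mean micturitions per 24 hours, "Change from baseline at the end of the 12-week treatment period adjusted for fluid intake". The protocol lists the same endpoint in Section 3 (Table 5) and Section 9.4.3.

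**Responder classes.** SAP 5.3.1 computes a percent change R in daytime incontinence episodes from the total over the 7-day period before the visit and the corresponding baseline total, with no division by days. A partial responder has R of -50% or lower but above -100%. If the baseline number is zero, 0.5 is added to it. SAP Section 5 accepts a diary with at least 4 valid days and uses at most 7. SAP 5.2.3 divides the same daytime episodes by the number of valid diary days.

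**The concern.** A fluid-adjusted change should be what remains after the effect of changed intake is removed. SAP 5.3.4 attaches that name to the part that should be removed. A programmer who follows the definition would report a change in voided volume as a fluid-adjusted change in frequency. It would show nothing when void size improved at constant volume, and a benefit when a child only drank less.

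In SAP 5.3.1 a total over fewer days is smaller even if the child leaks at the same daily rate. Whether a child falls on one side or the other of the 50% cut can therefore depend on how many days were recorded.

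**Working it through.** **1. The SAP's example (5.3.4).** Baseline: 5 voids on Saturday and 4 on Sunday, each 200 mL. Visit: 4 and 3 voids, each 250 mL.

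- TVV(baseline) = 9 × 200/2 = 900 mL; TVV(visit) = 7 × 250/2 = 875 mL; MVV(visit) = 250 mL. These match the SAP.
- Counts per 24 hours: 9/2 = 4.5 and 7/2 = 3.5; observed change 3.5 - 4.5 = -1.0.
- Expected count at baseline volume: 900/250 = 3.6, as in the SAP.
- Formula labelled as the adjusted change: (875 - 900)/250 = -0.1, as in the SAP.
- Change with volume held at baseline: 3.6 - 4.5 = -0.9.
- Check: -0.9 + (-0.1) = -1.0.

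Two illustrations with assumed volumes, both starting from 9 voids of 140 mL (1260 mL):

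| Case | Formula in 5.3.4 | Change at baseline volume |
|---|---|---|
| Volume unchanged, mean void 180 mL | (1260 - 1260)/180 = 0.0 | 1260/180 - 9 = -2.0 |
| Volume down 20% to 1008 mL, mean void unchanged | (1008 - 1260)/140 = -1.8 | 1260/140 - 9 = 0.0 |

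**2. Mean void size.** The split holds only if TVV/MVV equals the count. Take Saturday 4 × 200 mL and Sunday 8 × 100 mL: 800 mL and 6 voids per 24 hours. The pooled mean is 1600/12 = 133.3 mL, and 800/133.3 = 6.0. The mean of the two daily means is 150 mL, and 800/150 = 5.33.

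**3. Responder percentage (5.3.1).** Let nb and nx be the recorded days at baseline and visit, and r the true fall in daily rate. Raw totals give R = (nx/nb)(1 - r) - 1, so the 50% cut is reached at r = 1 - 0.5 nb/nx.

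| Days, baseline then visit | R at unchanged rate | True fall needed for R = -50% |
|---|---|---|
| Equal | 0% | 50.0% |
| 7 then 6 | -14.3% | 41.7% |
| 6 then 7 | +16.7% | 57.1% |
| 7 then 4 | -42.9% | 12.5% |
| 4 then 7 | +75.0% | 71.4% |

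Whole-number cases:

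- 14 episodes in 7 days, then 7 in 6 days: raw (7 - 14)/14 = -50%, partial responder; per day (7/6)/(14/7) - 1 = -41.7%, non-responder.
- 12 episodes in 6 days, then 7 in 7 days: raw (7 - 12)/12 = -41.7%, non-responder; per day (7/7)/(12/6) - 1 = -50%, partial responder.

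Zero episodes give R = -100% on either scale.

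For scale, assume Poisson counts, 1 to 3 episodes per day at baseline and a true 40% fall (400,000 simulated pairs per setting). With 7 then 6 days, raw totals put 50% to 54% of children at or beyond -50%, and daily means 33% to 43%. With 7 days at both visits the share is already 34% to 44%, from chance variation alone.

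**4. Two traps in the repair of 5.3.1.**

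- *Zero-baseline constant.* Take 0 episodes in 7 baseline days and 1 in 7 visit days, with 0.5 used as the baseline value. The present rule gives (1 - 0.5)/0.5 = +100%. Adding 0.5 to the daily mean would give (1/7 - 0.5)/0.5 = -71%, so a child who worsened would become a partial responder. Adding 0.5 to the total and then dividing gives (1/7)/(0.5/7) - 1 = +100%.
- *Dry weekends.* For incontinence, SAP Section 5 makes a weekend day valid only if a leak is recorded. Take 7 episodes in 7 baseline days, then 3 on weekdays and a dry weekend. Over 7 recorded days R = 3/7 - 1 = -57.1%; over the 5 days that qualify as valid, R = 3/5 - 1 = -40.0%.

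**The case against.** **The planned outputs are right.** SAP 6.4.3 asks for the count at baseline volume (3.6 in the example) and the observed-minus-expected difference (-0.1). Both are correctly labelled, as is the last line of the worked example. This stands. A reader might infer that the SAP's arithmetic is wrong or that the planned tables will mislead; the documents do not support that. What remains is one definition that contradicts its own section and a listed endpoint with no other definition. The adjusted change can be recovered by subtracting the baseline count from the planned level, so no data are lost.

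**Mean void size is already clear.** A reader might infer from SAP 5.2.1, where mean volume "will be calculated as the mean value of the mean volumes voided on each of the two days", that 5.3.4 uses the wrong mean. But the formula in 5.3.4 names mean volume per micturition and does not refer to 5.2.1. This stands too, so the pooled mean is only a clarification.

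**The responder effect has no known frequency.** It needs unequal day counts, and the documents do not say how common they are. Protocol 12.2.4 also monitors missing diary data at weeks 4, 8 and 12. Both points stand. A reader might infer a biased treatment comparison; that would need day counts to differ by arm, which nothing in the documents shows. If they are alike in both arms, the result is extra misclassification in both.

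**The repaired denominator would differ from that of SAP 5.2.3.** It would, because 5.2.3 keeps the valid-day rule. Whether that rule suits the secondary endpoint is a separate question.

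**Conclusion.** Both derivations are wrong as written, and the matter is minor. In 5.3.4 the term labelled as the adjusted change is the fluid component: -0.1 in the SAP's example, against -0.9 for the change at baseline volume. This follows from the SAP's own figures without further assumptions. In 5.3.1, R is exact when the same number of days is recorded at both visits. Otherwise, at an unchanged daily rate, it is off by -14% or +17% for a 7-day and a 6-day diary, and by -43% or +75% at the extremes the SAP accepts. Apart from chance zeros in short diaries, only the cut between partial responder and non-responder is affected. The range follows from the rules; the number of children affected cannot be derived from the documents.

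Both endpoints are exploratory and are only summarised. The primary and secondary analyses do not use either derivation.

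**What to change.** **SAP 5.3.4 and 6.4.3.** Define the fluid-adjusted change as TVV(baseline)/MVV(visit) minus baseline micturitions per 24 hours. Relabel the present formula as the fluid component (observed minus expected). Add the adjusted change to the summaries in 6.4.3. As a clarification, take counts and volumes from the same weekend voids with a recorded volume, since SAP 5.1 also counts voids without one, and set MVV to total recorded volume divided by the number of those voids.

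**SAP 5.3.1.** Compute R from mean daytime episodes per recorded diary day at both visits. Count a weekend day as recorded if it has at least one voided volume above zero, whether or not a leak is entered, so that dry weekend days stay in the denominator. Do not use the incontinence valid-day rule here. For a zero baseline, add 0.5 to the baseline total before dividing by baseline diary days; do not add it to the daily mean.

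The cost is SAP wording and programming for two exploratory endpoints. No further data are needed.

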5.3.5 Mean Number of Micturitions per 24 hours (adolescents only)

See Section 5.1.

5.3.6 Mean Volume Voided per 24 hours (adolescents only)

See Section 5.2.1.

5.3.7 Maximum Volume Voided (adolescents only)

See Section 5.2.2.

5.3.8 Mean Number of Incontinence Episodes per 24 hours (adolescents)

See Section 5.2.3.

5.3.9 Mean Number of Daytime Micturitions per 24 hours (adolescents only)

See Section 5.2.4.

5.3.10 Number of Dry (incontinence-free) Days per 7 Days at the End of the 12-weeks Treatment Period (adolescents only)

See Section 5.2.5.

5.3.11 Mean Number of Daytime Grade 3 or 4 (PPIUS) Urgency Episodes per 24 hours (adolescents only)

Result is obtained from "PPIUS-Urgency of the Micturition" from 2-day Weekend Episodic Diary.

Scoring PPIUS scale:

- Grade 0: No urgency I felt no need to empty my bladder, but did so for other reasons
- Grade 1: Mild urgency I could postpone voiding as long as necessary, without fear of wetting myself
- Grade 2: Moderate urgency I could postpone voiding for a short while, without fear of wetting myself
- Grade 3: Severe urgency I could not postpone voiding, but had to rush to the toilet in order not to wet myself
- Grade 4: Urge incontinence I leaked before reaching the toilet

Let N_{34} equal the number of times that an adolescent subject recorded a grade 3 or 4 urgency on a diary day. If there are no grade 3 or 4 urgency episodes on a valid diary day, then N_{34} equals 0. For each subject, the mean number of grade 3 or 4 urgency episodes per 24 hours, at Visit x (x=4, 5, 6, and 7), is the mean of N₃₄ over the valid diary days of the 2-day Weekend Episodic Diary.

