| To evaluate the efficacy of mirabegron in pediatric subjects (5 to < 18 years) with OAB | Percentage of subjects with a reduction in daytime incontinence episodes (< 50% reduction [nonresponder], 50% [partial responder] and 100% [responder]) Improvement from baseline in worst incontinence grading Change from baseline at the end of the 12-week treatment period adjusted for fluid intake: Mean number of micturitions per 24 hours Change from baseline at the end of the 12-week treatment period (adolescents only): Mean number of micturitions per 24 hours Mean number of daytime micturitions per 24 hours Mean volume voided per 24 hours Mean number of incontinence episodes per 24 hours Number of dry (incontinence-free) days per 7 days at the end of the 12-week treatment period (adolescents only) Mean number of daytime grade 3 or 4 (PPIUS) urgency episodes per 24 hours (adolescents only) |

AE: adverse event; ECG: electrocardiogram; OAB: overactive bladder; PPIUS: patient perception of intensity of urgency scale; PVR: post void residual.

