5 EFFICACY AND SAFETY ENDPOINTS

Data for the efficacy endpoints will be recorded on an e-diary. This e-diary consists of a:

- 5-day Weekday Diary (bladder diary, Monday Friday), which is used for a 5-day period to record micturition frequency and incontinence episodes, and
- 2-day Weekend Episodic Diary (Saturday and Sunday), which is used to record micturition frequency, incontinence episodes, (pee) volume measurements, and worst leakage severity.

A valid diary day for:

• "Volumes"

In the 2-day Weekend Episodic Diary, is any e-diary day for which at least one "Pee Volume" greater than 0 mL is recorded with complete date and time.

- "Micturitions"
- In 2-day Weekend Episodic Diary, is any diary day for which at least once "Pee Volume" greater than 0 is recorded.
- In 5-day Week Diary, is any diary day for which the response to the question "Number of times using the toilet during the day/night" is not missing.
 - "Incontinence episodes"
- In 2-day Weekend Episodic Diary, is any diary day for which at least:
 - One micturition ("Pee Volume" >0) and
 - One "Leakage" or "Pee in toilet and Leakage" are recorded.
- In 5-day Week Diary, is any diary day for which:
 - The response to the question "How was your day/night" is not missing.

A valid diary for an analysis visit is a diary with at least 4 valid diary days within that analysis visit window. If for more than 7 days the diary is filled in prior to a visit, only the last 7 days prior to that visit will be used for calculation of the efficacy endpoints.

The number of valid diary days: Count of the valid diary days during the 7-day diary period. Days of visits to the clinic will not be counted as valid diary days.

In the event that in the 2-day Weekend Episodic Diary there are two entries with the same collection date and time but with different times of entry on the device, the last entry (time) will be used for analysis.

For several of the secondary efficacy endpoints, diary data will be classified as either "daytime" or "nighttime", where "daytime" is considered to mean "between waking up in the morning and going to sleep later the same day or next day" and "nighttime" means "between going to sleep on a day and waking up on the same or next day".

Whether an entry into the 5-day Week Diary is done during daytime or nighttime is captured on this diary.

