5.2.3 Mean Number of Daytime Incontinence Episodes per 24 hours

For a week day the number of Incontinence Episodes per 24 hours will be derived from "Number of Leakages During the Day" and "Number of Leakages During the Night" of the 5-day Week Diary. Incontinence episodes on measuring days will be classified as daytime or nighttime episodes as entered in the 5-day Week Diary.

For a weekend day the number of incontinence episodes will be derived from the times a "Leakage" or a "Pee in Toilet and Leakage" was entered into the 2-day Weekend Episodic Diary. Whether an Incontinence Episode was during daytime or nighttime will be based on the time-points the subject went to sleep and woke-up.

For each subject, the mean number of incontinence episodes per day/night (during the day/night) at Visit x (x=4, 5, 6, and 7) will be calculated using all available (non-missing) number of incontinence episodes for the valid diary days in the 5-day Week Diary and in the 2-day Weekend Episodic Diary for daytime in the 7-day period before the visit:

Mean No. of Daytime Incontinence Episodes at Visit x =

Total number of "Daytime Leakage Counts" over the Valid Diary Days prior to Visit x Number of Valid Diary Days

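### The adolescent daytime-urgency endpoint is derived as a whole-day count, and the adolescent 24-hour incontinence endpoint refers to a section whose only visit-level formula counts daytime leaks

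*SAP*

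**What the plan says.** **Urgency.** The protocol (Section 3, Table 5) lists the adolescent endpoint as "Mean number of daytime grade 3 or 4 (PPIUS) urgency episodes per 24 hours (adolescents only)". The heading of SAP 5.3.11 and the analysis list in SAP 6.4.3 ("Mean number of daytime grade 3 or 4 on Patient Perception of Intensity of Urgency Scale (PPIUS) urgency episodes per 24 hours") also say daytime. The derivation in SAP 5.3.11 uses only the 2-day Weekend Episodic Diary. It defines N34 as the number of times an adolescent "recorded a grade 3 or 4 urgency on a diary day", and then defines "the mean number of grade 3 or 4 urgency episodes per 24 hours, at Visit x" as the average of N34 over the valid weekend diary days. Neither sentence mentions waking or sleeping times, and the word daytime is absent from the second.

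**Incontinence.** For children, the protocol lists daytime and nighttime incontinence as separate endpoints. For adolescents it lists one endpoint, episodes per 24 hours. SAP 5.3.8 keeps the 24-hour name, and its entire text is "See Section 5.2.3". SAP 5.2.3 is the daytime incontinence section. The numerator of its one visit-level formula is "Total number of 'Daytime Leakage Counts' over the Valid Diary Days prior to Visit x", and the denominator is the number of valid diary days.

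**Day/night classification.** SAP Section 5 introduces it with "For several of the secondary efficacy endpoints, diary data will be classified as either" daytime or nighttime. It adds that weekend entries are classified from the subject's sleep and wake times, with an imputed bedtime on Sunday.

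**The concern.** In each case the endpoint's name and its derivation describe different quantities. A programmer who follows SAP 5.3.11 literally produces a whole-day urgency count under a daytime label. One who follows the formula in SAP 5.2.3 produces a daytime leak count under a 24-hour label. The discrepancies run in opposite directions: night urgency is counted where the name excludes it, and night leaks can be omitted where the name includes them.

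Adolescent efficacy is summarised descriptively only (SAP 6.4 and 6.4.3). No model or test sits behind these tables, so a reader relies on the label to know what was measured.

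**Working it through.** There is no document figure to reproduce. The check sets each name against its rule and then sizes the gap under a stated assumption.

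**Step 1: urgency.** The SAP states the waking-hours limit where it applies one. SAP 5.2.4 (daytime micturitions) counts weekend voids after waking and up to going to sleep, and treats the first void at or after waking as nighttime, as SAP 5.1 does. SAP 5.3.1 (daytime leaks, responder endpoint) also limits weekend entries to the interval from waking to sleep. SAP 5.3.11 has no such limit. The classification in SAP Section 5 is introduced for secondary endpoints, whereas this endpoint is exploratory. As written, N34 is a whole-diary-day count.

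**Step 2: incontinence.** SAP 5.2.3 contains:

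- a weekday count per 24 hours, built from the day and night leak fields;
- a weekend count of all leak entries, then classified by sleep and wake times;
- a lead-in that mentions day and night but ends by restricting the average to daytime;
- one formula: daytime leaks divided by valid diary days.

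The ingredients of a 24-hour mean are present, but the mean is not written there or in any other section.

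**Step 3: consistency with dry days.** The adolescent dry-days endpoint (SAP 5.3.10, referring to 5.2.5) treats a weekday as wet if either the day or the night was wet, and a weekend day as wet if any leak is reported. Under the printed formula, an adolescent who leaks every night and never by day would have 0 incontinence episodes per 24 hours and also 0 dry days.

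**Step 4: size.** Let s be the share of episodes at night. This is an assumption, because the documents give no day/night rates.

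- Urgency: whole-day count / daytime count = 1/(1 − s).
- Incontinence: daytime mean / 24-hour mean = 1 − s.

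| assumed s | urgency as written / daytime | incontinence by formula / 24-hour |
|---|---|---|
| 10% | 1/0.90 = 1.11 | 90% |
| 20% | 1/0.80 = 1.25 | 80% |
| 30% | 1/0.70 = 1.43 | 70% |

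Two worked cases, also with assumed counts:

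- Urgency: 3 daytime and 1 night grade 3 or 4 episodes on each of 2 weekend days give 8/2 = 4.0 as written and 6/2 = 3.0 with a daytime limit.
- Incontinence: 10 daytime and 4 night leaks over 7 valid days give 10/7 = 1.43 by the formula and 14/7 = 2.00 as a 24-hour mean.

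If the micturition rule governs urgency, a grade 3 or 4 first morning void counts as nighttime. The two urgency counts could then differ by one episode a day even in an adolescent who never voids during sleep.

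**The case against.** The best defence concerns incontinence. A reader might infer that SAP 5.3.8 requires night leaks to be dropped. The text does not go that far: SAP 5.2.3 opens with a day-plus-night weekday count, gathers all weekend leaks and supplies the denominator, and its formula carries the daytime endpoint's name. A programmer guided by the title of SAP 5.3.8 could build the right variable. This half is therefore a mis-targeted and incomplete cross-reference. It still needs correcting, because the only formula at the target gives the wrong quantity.

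For urgency, the defence is that the heading says daytime and that Section 5 explains how weekend entries are classified, so a definition exists. That is true, but the N34 rule does not invoke it, and the SAP states the limit explicitly for other daytime counts. This half stands.

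Three further points are fair:

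- A reader might take these two measures to be the whole of the adolescent efficacy evidence. They are not. SAP 5.3 also lists micturitions, daytime micturitions, mean and maximum volume voided and dry days, and dry days and worst incontinence grade use night data.
- Any single percentage error rests on chosen counts, so only a range under an assumed s is defensible.
- The same rule applies to both arms and all visits. The fault changes what is measured and does not by itself favour one arm.

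**Conclusion.** The urgency derivation is wrong as written: it gives a whole-day mean under a daytime name. The incontinence derivation is incomplete: it refers to a daytime-only formula, and no 24-hour visit mean is defined anywhere. For an assumed night share of 10% to 30%, urgency is overstated 1.11 to 1.43 times, and incontinence under the printed formula is 90% to 70% of its 24-hour value. The range rests entirely on that assumption, and the incontinence figure applies only if the printed formula is the one programmed.

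The consequence is minor. Both are exploratory, descriptive endpoints in adolescents, and the primary analysis in children, its type I error and the sample size are untouched.

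**What to change.** **SAP 5.3.11.** Restrict N34 to daytime using the micturition rule of SAP 5.1 and 5.2.4: entries after wake-up and up to going to sleep, with the first void at or after waking counted as nighttime and the Sunday bedtime imputed as in Section 5. The micturition rule is a better model than the leak rule of SAP 5.3.1 because PPIUS is scored per micturition. A plain wake-to-sleep limit could count the first morning void as daytime for urgency while SAP 5.2.4 counts it as nighttime.

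**SAP 5.3.8.** Replace the cross-reference with its own formula: (daytime + nighttime leakages over valid diary days) / number of valid diary days.

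**Cost.** Two derivation lines and no new data. Sunday bedtime is not captured in the diary, so the Sunday half of the urgency split relies on the imputation the SAP already uses: evening self-measured blood pressure time plus 1 hour, or 23:59 if that time is missing. The change should be made before database hard lock.
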